## **III. NON-THERAPEUTIC BIOMEDICAL RESEARCH INVOLVING HUMAN SUBJECTS (Non-Clinical Biomedical Research)**

1. In the purely scientific application of medical research carried out on a human being, it is the duty of the physician to remain the protector of the life and health of that person on whom biomedical research is being carried out.
2. The subject should be volunteers - either healthy persons or subjects for whom the experimental design is not related to the subject's illness.

3. The investigator or the investigating team should discontinue the research if in his/her or their judgment it may, if continued, be harmful to the individual.
4. In research on man, the interest of science and society should never take precedence over considerations related to the wellbeing of the subject.

**Appendix 2. Study Drug (dalteparin sodium) Dosing Calculation Examples (Additional dosing administration instructions can be found in the Investigational Product (IP) Manual)**

**Example:** Subject DOSING LEVEL (IU/kg) X Pt Weight (kg) = Dose to administer (IU)  
 Dose to administer (IU)/Drug concentration (IU/mL) = Volume to administer (mL)

Protocol Age Group	Example Patient Age	Required Starting Dose	Example weight (kg)	Dose to Administer (IU)	Drug Concentration* Used (IU/mL)	Volume to Administer (mL)
0 to <8 Weeks	4 wks	125 IU/kg	4 kg	500 IU	2500 IU/mL PF	0.2 mL
≥8 Weeks to <2 Years	10 wks	150 IU/kg	7 kg	1050 IU	2500 IU/mL PF	0.42 mL
≥2 years to <8 Years	3 yrs	125 IU/kg	12 kg	1500 IU	2500 IU/mL PF	0.6 mL
≥8 Years <12 Years	8 yrs	125 IU/kg	24 kg	3000 IU	10,000 IU/mL PF	0.3 mL
≥12 Years <19 years	15 yrs	100 IU/kg	82 kg	8200 IU	10,000 IU/mL PF	0.82 mL
≥12 Years <19 years	15 yrs	100 IU/kg	82 kg	8200 IU	25,000 IU/mL	0.33 mL

- \*Important to note the concentration of dalteparin sodium being used in order to determine the correct volume to administer to the subject

### Appendix 3. Dalteparin Simulation Strategy

#### Background:

In support of this trial, simulations of dalteparin activity (anti-Xa activity) in response to SC administration are suggested to support the sampling scheme and sample size requirements. Simulations will be based on a nonlinear mixed effect model defined in the NONMEM algorithm and constructed for an analysis of children at increased risk for TE receiving once-daily SC dalteparin. The analysis of these study results (n=43 subjects/31 evaluable), suggests that differences in the rate of uptake of dalteparin may be expected across various age strata. This effect was evaluated by the calculation of the time of maximum anti-Xa activity (Tmax) across the age group. In this situation Tmax serves as a surrogate for absorption rate (ka) as there was little data collected with the sparse sampling scheme during the absorption phase. Likewise, simulations for this study will consider various sampling schemes and examine the bias and precision in key PK parameters (principally CL and Vd but including ka) as well as the likely sample size required to demonstrate a statistical difference in Fragmin® anti-Xa clearance in pediatric versus adult populations.

#### Plan:

Two sampling designs will be considered:

1. Blocked randomization design: This design will consider the randomization of subjects into single sample collection groups within age strata (4, 7, 12 and 24 hour collections) for each age range category.
2. Two-sequence, two-sample randomization design: This design will consider randomization to two different sampling windows (1 to 3 h, 5 to 8 h or 3 to 5 h, 8 to 12 h).

Demographic data from the pediatric TE study will be used as sampling characteristics for the various age strata. The population model will be used to simulate anti-Xa activity profiles for each of the proposed sampling schemes for sample sizes of 10, 20, 30 and 40 subjects per strata. One hundred trials for each of sample size and scheme scenario will be simulated (4x2x100 = 800 simulated trials). Data will be refit to the population model and bias and precision of PK parameters will be evaluated. The impact of sample size to detect a 30% difference in CL between historical adult values will also be examined.

---

 Barrett JS, Mitchell LG, Patel D, et al. A Population based Analysis of Dalteparin Pharmacokinetics in Pediatric Patients at Risk for Thromboembolic Events. *Abstract submitted (American College of Clinical Pharmacology)*.

#### **Appendix 4. Regional Amendment for Highly Effective Methods of Contraception**

As per the European Heads of Medicines Agency's Clinical Trial Facilitation Group's recommendation (Recommendations related to contraception and pregnancy testing

in clinical trials – Final Version 2014-09-15) any European Union Member State or other country that follows these recommendations and does not recognize condoms with spermicide as a highly effective method of contraception will follow the highly effective methods of contraception as indicated below in the revised Section 9.1.5, Pregnancy Test.

##### **9.1.5. Pregnancy Test**

For female subjects of childbearing potential, a serum or urine pregnancy test, with sensitivity of at least 25 IU/mL, will be performed at screening, before investigational product administration at the Baseline visit, unless the Baseline visit is conducted within 2 days of the Screening Visit, and at all other study visits. During the Dose Adjustment Phase, if multiple study visits are conducted, the pregnancy test will only be required once in the 7-day Dose Adjustment period. A negative pregnancy result is required before the subject may receive the investigational product. Pregnancy tests will also be done whenever 1 menstrual cycle is missed during the active treatment period (or when potential pregnancy is otherwise suspected), and repeated at follow up visits and at the end of the study to confirm the subject has not become pregnant during the study. Pregnancy tests may also be repeated as per request of institutional review boards (IRBs)/ethics committees (ECs) or if required by local regulations.

In the case of a positive confirmed pregnancy, the subject will be withdrawn from administration of investigational product and from the study.

All male subjects who are able to father children and female subjects who are of childbearing potential and are sexually active and at risk for pregnancy must agree to use a highly effective method of contraception consistently and correctly for the duration of the active treatment period and for at least 28 days after the last dose of investigational product. The investigator or his or her designee, in consultation with the subject, will confirm that the subject has selected an appropriate method of contraception for the individual subject and his or her partner from the permitted list of contraception methods (see below) and instruct the subject in its consistent and correct use. Subjects need to affirm that they meet the criteria for correct use of at least 1 of the selected methods of contraception. The investigator or his/her designee will discuss with the subject the need to use highly effective contraception consistently and correctly according to the schedule of activities and document such conversation in the subject's chart. In addition, the investigator or his or her designee will instruct the subject to call immediately if the selected contraception method is discontinued or if pregnancy is known or suspected in the subject or the subject's partner.

Highly effective methods of contraception are those that, alone or in combination, result in a failure rate of less than 1% per year when used consistently and correctly (ie, perfect use) and include the following:

1. Use of oral, inserted, injected, implanted or transdermal hormonal methods of contraception is not allowed due to risks of VTE.
2. Correctly placed copper containing intrauterine device (IUD).
3. Male sterilization with absence of sperm in the post-vasectomy ejaculate.
4. Bilateral tubal ligation / bilateral salpingectomy or bilateral tubal occlusive procedure (provided that occlusion has been confirmed in accordance with the device's label).

Female partner who meets the criteria for non-childbearing potential, as described below:

Female subjects of non-childbearing potential must meet at least one of the following criteria:

- Have undergone a documented hysterectomy and/or bilateral oophorectomy;
- Have medically confirmed ovarian failure; or

NOTE: Sexual abstinence, defined as completely and persistently refraining from all heterosexual intercourse (including during the entire period of risk associated with the study treatments) may obviate the need for contraception ONLY if this is the preferred and usual lifestyle of the subject. If this option is selected for a female subject of childbearing potential, then the subject would be required to undergo interval urine pregnancy testing (specify a schedule) and would be asked to record stop and start dates for menstruation throughout the course of the study.

The use of oral, inserted, injected, implanted or transdermal hormonal methods of contraception are not allowed due to risks of VTE. If a subject was using a hormonal based contraceptive prior to study entry, it should be discontinued prior to study entry. There is no required wash-out period required for recently discontinued hormonal based contraception.

All other female subjects (including females with tubal ligations) will be considered to be of childbearing potential. All sexually active male subjects must agree to prevent potential transfer of and exposure to drug through semen to their partners by using a condom consistently and correctly, beginning with the first dose of investigational product and continuing for at least 28 days after the last dose.

## 1. VERSION HISTORY

**Table 1. Summary of Major Changes in SAP Amendments**

SAP Version	Change	Rationale
1	Not Applicable	Not Applicable
2	Administrative Changes due to protocol amendments	
Transition of study to Pfizer Inc from Eisai; Updating of Safety Section per Pfizer safety reporting processes and procedures, and other relevant sections per Pfizer Inc processes and procedures
 
Include protocol modifications endorsed by FDA in a Type C Meeting conducted on 05 November 2015, including updating age cohort groups, inclusion of all patients with VTE and removal of the central imaging reader and Adjudication Committee

## 2. INTRODUCTION

*This protocol implements a post approval clinical commitment between Pfizer Inc., and the Food and Drug Administration (FDA) relating to the dalteparin sNDA 20-287/S-035, “for the extended treatment of symptomatic venous thromboembolism [VTE (proximal deep vein thrombosis [DVT] and/or pulmonary embolism [PE])] to reduce recurrent VTE in subjects with cancer”. This phase II pharmacodynamic (PD) study is intended to provide information to guide the conditions under which dalteparin may be used for the treatment of acute and secondary prophylaxis of VTE in children. The PD profiles for treatment doses of dalteparin using anti-Xa levels will also be assessed in a population PD analysis methodology.*

### 2.1. Study Objectives

**The primary objective of this study is to:**

- *To determine the PD profiles for treatment doses of dalteparin in pediatric subjects of different ages with venous thromboembolism (VTE), and with or without cancer, using anti-Xa (Xa) levels and a population PD analysis methodology.*
- *To determine the median dose (IU/kg) required to achieve therapeutic anti-Xa levels (0.5-1.0 IU/mL) based on subject age and weight.*

[figure not shown]
**Secondary objectives will be:**

- *To assess the proportion of subjects with major bleeding events during dalteparin treatment.*
- *To assess the proportion of subjects with minor bleeding events during dalteparin treatment.*
- *To explore the proportion of subjects with objectively documented new or progressive symptomatic VTE during dalteparin treatment.*
- *To explore the relationships of recurrent VTE and major bleeding events with anti-Xa levels if data permits.*
- *To assess proportion of subjects achieving an anti-Xa therapeutic range of 0.5 to 1.0IU/mL during the Dose Adjustment Phase.*
- *To explore the proportions of subjects with progression, regression, resolution or no change in the qualifying VTE during dalteparin treatment.*
- *To describe the overall safety profile of dalteparin in pediatric subjects of different ages with VTE.*

**2.2. Study Design**

*The study is a 3 month prospective, multicenter, open-label cohort study in North America and Europe to determine twice daily dosing recommendations of dalteparin as a function of age in order to achieve anti-Xa levels of 0.5 to 1.0 IU/mL at 4 hour postdose in children with or without various cancers and requiring anticoagulation for the treatment and secondary prophylaxis of VTE. The study is divided into 3 phases (Figure 1): 1) Dose Adjustment Phase of up to 7 days; 2) PD Phase; and 3) Follow-up Phase, to complete up to 90 days of treatment.*

**Figure 1. Schematic Trial Design**

Subjects will be enrolled into one of the following five age groups (cohorts): newborn (0-<8 weeks), infants (>=8weeks - <2 years), preschool (>=2 years - <8 years), school (>= 8 years - < 12 years), and teen (>= 12 years - < 19 years).

The target enrollment is a total of 50 subjects who have completed the PD Phase.

All age groups will receive dalteparin twice daily. The initial dose for each age group are: 125 IU/kg for 0 to <8 weeks, 150 IU/kg for  $\geq$ 8 weeks to < 2 years, 125 IU/kg for  $\geq$ 2 weeks to < 8 years and  $\geq$ 8 years to < 12 years, and 100 IU/kg for  $\geq$ 12 years to <19 years.

The Dose Adjustment Phase will begin following the first dose and continue for up to 7 days. During the Dose Adjustment Phase, doses are adjusted according to anti-Xa levels. The first anti-Xa level may be taken 4 hours  $\pm$ 1 hour after the first, second or third dose per institutional standard. Subsequent anti-Xa levels will be drawn at 4 hours  $\pm$ 1 hour postdose. Doses will be adjusted in increments or decrements of 25 IU/kg in order to achieve target anti-Xa levels (0.5-1.0 IU/mL).

Subjects completing the Dose Adjustment Phase will enter into the PD Phase and continue on the final twice daily dosing (Q12h  $\pm$ 1 hour) regimen from the Dose Adjustment Phase. The PD Phase will last for up to 7 days in order to complete two PD samples. After subjects successfully complete the PD Phase, they will enter the Follow-up Phase.

During this phase, subjects will continue receiving twice daily dalteparin q12h ( $\pm$ 1 hour) and will be followed according to the visit schedule. The maximum duration is 90 days after first dose of dalteparin.

### **3. ENDPOINTS AND BASELINE VARIABLES: DEFINATIONS AND CONVENTIONS**

#### **3.1. PD Endpoint(s)**

##### **3.1.1. Primary PD Endpoints**

- Anti-Xa activity versus time profile following dalteparin treatment in pediatric subjects of different ages with VTE.

Note: This is beyond the scope of the SAP and it will be detailed in a separated population modeling analysis plan (PMAP-EQDD-A630c-DP4-560).

- Median dose required per age group to achieve an anti-Xa level of 0.5 to 1.0 IU/mL during the dose adjustment phase.

##### **3.1.2. Secondary PD endpoints**

- Proportion of children achieving an anti-Xa therapeutic range of 0.5 to 1.0 IU/mL during the Dose Adjustment Phase.
- Proportion of subjects who remain within therapeutic range during the follow up phase (Visit 5, Visit 6 and Visit 7).
- The percentage of anti-Xa levels measured 4 hours post dose  $\pm$ 1 hour that are outside the target range will be calculated during the follow up phase of study (Visit 5, Visit 6 and Visit 7).

- The maintenance dose, time to achieve the target range, and number of dose adjustment during dose adjustment phase.

### **3.2. Efficacy Endpoint(s)**

All efficacy endpoints are secondary endpoints.

- Proportion of subjects with objectively documented new or progressive symptomatic VTE during dalteparin treatment.
- Relationship between objectively documented new or progressive symptomatic VTE and the anti-Xa level during dalteparin treatment if data permits.
- The proportions of subjects with progression, regression, resolution or no change in the qualifying VTE during dalteparin treatment.
- Time to first episode of symptomatic recurrent VTE during dalteparin treatment.

### **3.3. Baseline Variables**

#### **3.3.1. Stratification and Randomization**

Enrolled subjects who achieve the target therapeutic anti-Xa level in Dose Adjustment Phase will advance to the PD phase. These subjects will be centrally randomized (at baseline) to two different blood sampling scheme (1-3 h & 5-8 h or 3-5 h & 8-12 h) for the PD phase with a ratio of 1:1 and the randomization will be blocked and stratified by age group.

#### **3.3.2. Covariates**

As an objective of the study is to examine safety and efficacy within different age groups, subjects will be presented split into the age categories: 0-<8 weeks, >=8weeks - <2 years, >=2 years - <8 years, >= 8 years - < 12 years, and >= 12 years - < 19 years.

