**Figure 1. Chemical Structure of Dalteparin Sodium**

### 3.2. Rationale

Dalteparin sodium (Fragmin®) is a low molecular weight heparin (LMWH), produced by degradation of heparin, a member of the glycosaminoglycan (GAG) family of biological entities found in the intestinal mucosa. Dalteparin was first approved in the US in December 1994 for primary prophylaxis of DVT in subjects undergoing abdominal surgery. This was followed by approvals for primary prophylaxis of DVT in subjects undergoing hip surgery and in medical subjects with severely restricted mobility during acute illness. Dalteparin sodium is also indicated for the prophylaxis of ischemic complications in unstable angina and non-Q-wave myocardial infarction, when concurrently administered with aspirin therapy.

Dalteparin was approved in 2006 for the extended treatment of VTE in adult patients (age  $\geq 18$  years) with cancer. For these indications, dalteparin has an acceptable safety profile. Further information regarding dosage, safety profile, etc., can be found in the current US Package Insert or local Summary of Product Characteristics, which will serve as the Investigators' Brochure for this study.

Multiple retrospective studies have shown that cancer-associated thrombosis (CAT) is a significant entity previously under recognized and under treated. When compared to subjects without cancer, cancer subjects are far more prone to develop VTE; in fact, VTE may represent the initial presenting finding for an otherwise occult cancer. When compared to cancer-free subjects with symptomatic VTE, cancer subjects with VTE are more prone to recurrence and to treatment-related bleeding complications.

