#### 4. STUDY OBJECTIVES AND ENDPOINTS

The primary objective of this study is to:

- To determine the PD profiles for treatment doses of dalteparin in pediatric subjects of different ages with or without cancer and VTE, using Anti-Xa levels and a population PD analysis methodology;
- To determine the median dose (IU/kg) required to achieve therapeutic Anti-Xa levels (0.5-1.0 IU/mL) based on subject age and weight.

Secondary objectives will be:

- To assess the proportion of major bleeding events during dalteparin treatment;
- To assess the proportion of minor bleeding events during dalteparin treatment;
- To explore the proportion of objectively documented new or progressive symptomatic VTE during dalteparin treatment;
- To explore the relationships of recurrent VTE and major bleeding events with anti-Xa levels, if data permits;
- To explore the proportions of subjects with progression, regression, resolution or no change in the qualifying VTE during dalteparin treatment;
- To describe the overall safety profile of dalteparin in pediatric subjects of different ages with or without cancer and VTE.
- To assess the proportion of subjects achieving an anti-Xa therapeutic range of 0.5 to 1.0 IU/mL during the Dose Adjustment Phase.

Primary Endpoints:

- Determine the median dose of dalteparin (IU/kg) associated with the achievement of the therapeutic Anti-Xa level (0.5-1.0 IU/mL) among subjects that achieved their therapeutic Anti-Xa level during the dose adjustment phase, for each age cohort group;
- Anti-Xa activity versus time profile following dalteparin treatment will be explored using a population PD analysis methodology. Population PD parameters such as clearance, volume of distribution, absorption rate constant will be estimated based on Anti-Xa levels collected during dose adjustment phase, PD phase and follow-up phase. Age and other relevant covariates will be explored in the population PD analysis.

Secondary Endpoints:

- Proportion of subjects achieving an Anti-Xa therapeutic range of 0.5 to 1.0 IU/mL during the Dose Adjustment Phase (up to 7 days);
- Proportion of subjects with objectively documented, new or progressive symptomatic VTE during dalteparin treatment utilizing the same objective technique performed at Baseline;
- Time to first episode of symptomatic recurrent VTE during dalteparin treatment;

[figure not shown]

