## 5. INVESTIGATIONAL PLAN

### 5.1. Overall Study Design and Plan – Description

The study is a 3-month prospective, multicenter, open-label cohort study in North America and Europe to determine twice daily dosing recommendations of dalteparin as a function of age in order to achieve Anti-Xa levels of 0.5 to 1.0 IU/mL at 4 hour ( $\pm$  1 hour) post-dose in children with or without various cancers and requiring anticoagulation for the treatment and secondary prophylaxis of VTE. The study is divided into 3 phases: 1) Dose Adjustment Phase of up to 7 days; 2) PD Phase; and 3) Follow-Up Phase, to complete up to 90 days of treatment for cancer patients and treatment of non-cancer patients should be aligned with the 2012 ACCP Guidelines which suggest a total duration of anticoagulation treatment of between 6 weeks and 3 months rather than shorter or longer durations (Grade 2C), following completion of the PD Phase. Non-cancer patients will be required to remain in the study, however, for the full 3 months to complete all remaining study visits, regardless of dalteparin treatment duration. For non-cancer patients who stop dalteparin treatment prior to 3 months, Anti-Xa and Anti-IIa plasma sampling will not be required after study medication discontinuation.

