### **12. STATISTICAL METHODS**

#### **12.1. Determination of Sample Size**

Subjects, with or without a diagnosis of various cancers within 6 months of the Screening Visit and requiring anticoagulation for the treatment and secondary prophylaxis of VTE, will be enrolled into the following five age groups:

- 0 to < 8 Weeks;
- $\geq$  8 Weeks to < 2 Years;
- $\geq$  2 Years to < 8 Years;
- $\geq$  8 Years to < 12 Years;

- $\geq 12$  Years to  $< 19$  Years.

Target enrollment is 50 subjects. A sample size of 50 subjects is sufficient to estimate Anti-Xa clearance and  $V_d$  of dalteparin. Enrollment will continue until 50 subjects have viable PD profiles after treatment doses of dalteparin.

The sample size was determined based on historical data and a population pharmacokinetic (PK)/PD model, evaluation of the effect of sample scheme and sample size per age stratum on the bias and precision of key PK/PD parameters, after evaluation of total N of 10, 20, 30, 40 and 50 (2, 4, 6, 8, 10 per age stratum as available) and evaluation of single and 2-point sample densities and impact of randomization across strata with 100 trial simulations per design examined. In addition, blood sampling density was also considered after the subject sample size was determined. Single-point sampling designs yielded unacceptable bias in total body clearance of the drug (CL) and/or  $V_d$ ; confounding of effects if blocked within stratum. Double sampling at 3, 8 and 5, 12 hours post-dose performs more efficiently. Therefore, randomized two-sample design per each subject was also determined.

See [Appendix 3](#) for additional information regarding the trial simulation strategy.

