#### **6.3.1. Safety analysis**

- Proportion of subjects with major bleeding assessed by investigators during dalteparin treatment.

The count and proportion will be summarized overall and by each age group, along with the two-sided exact 95% CI.

- Relationship between major bleeding event and the Anti-Xa level during dalteparin treatment.

Logistic regression for major bleeding event assessed by investigators on anti-Xa level observed at the end of dose adjustment and other prognostic factors (eg, age, gender), will be performed. For each of the covariates, the odds ratio, and the corresponding 95% CI, will be displayed.

Subjects who experience at least one major bleeding event while on study will be counted as Yes.

- Proportion of subjects with minor bleeding events during dalteparin treatment.

The count and proportion will be summarized overall and by each age group, along with the two-sided exact 95% CI.

- Time to first major bleeding event during dalteparin treatment.

The time to first major bleeding event assess by investigators will be described by using the Kaplan-Meier method. In addition, the Cox Proportional Hazard Regression model will be employed to assess the hazard ratio of the event with prognostic factors.

See [Appendix 1.1](#) for a general description of censoring of time-to-event variables.

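### On-treatment VTE and bleeding proportions have no cancer split or exposure adjustment, and the SAP's models do not reliably separate age from cancer status or treatment length

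*SAP*

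**What the plan says.** **Risk.** Protocol 3.2 states that, compared with cancer-free subjects, "cancer subjects with VTE are more prone to recurrence and to treatment-related bleeding complications". It gives no rate or ratio, and the statement is not specific to children.

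**Treatment length.** Protocol 5.1 divides the study into phases "to complete up to 90 days of treatment for cancer patients". For non-cancer patients it follows guidelines that "suggest a total duration of anticoagulation treatment of between 6 weeks and 3 months rather than shorter or longer durations". Non-cancer children who stop early stay in the study for the full 3 months.

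**Objective.** Protocol 4 lists, as a secondary objective, "To describe the overall safety profile of dalteparin in pediatric subjects of different ages with or without cancer and VTE". SAP 2.1 restates this objective without the reference to cancer.

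**Tables.** SAP 3.3.2 gives age as the only reporting factor: "subjects will be presented split into the age categories". For major and for minor bleeding, SAP 6.3.1 says "The count and proportion will be summarized overall and by each age group, along with the two-sided exact 95% CI". SAP 6.1.2.1 does the same for new or progressive VTE and for the outcome of the qualifying thrombus.

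**Models.** Both documents plan Kaplan-Meier and Cox analyses for recurrent VTE and major bleeding.
- Protocol: the synopsis names age group and baseline tumor type for the VTE Cox model. Sections 12.3.5 and 12.3.6 list them as examples for both Cox models and add chemotherapy status for bleeding.
- SAP: the Cox models name no factors. The VTE logistic model gives age and baseline tumor status as examples; the bleeding logistic model gives age and gender.

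**Censoring.** SAP Appendix 1.1 censors event-free subjects at the latest date in the database, expected to be the End of Study visit. Protocol 12.3.7 uses the last event assessment. Neither uses the end of treatment.

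**The concern.** Two things that drive an on-treatment event proportion, daily risk and days at risk, are expected or planned to differ between children with and without cancer. Enrolment is not balanced on cancer status within age groups; only the sampling schedule is randomised, stratified by age. If the cancer share differs by age, the by-age proportions mix age with cancer status and treatment length. SAP 3.3.2 says the age split is there to examine safety and efficacy within age groups, so these tables will be read that way.

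The pooled proportion has a related weakness: its value depends on the share of cancer children who happen to be recruited. In addition, the objective of describing safety with or without cancer has no endpoint table that shows the two groups apart.

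**Working it through.** **1. The plan's own figure.** Protocol 12.1 says "A sample size of 50 subjects is sufficient to estimate Anti-Xa clearance and" volume of distribution, after simulating "2, 4, 6, 8, 10 per age stratum as available". Five strata × 10 = 50, which agrees. The simulation's parameters are not given, so it cannot be rerun. No event rate, precision or power is stated for VTE or bleeding, so there is no figure to reproduce for these endpoints.

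**2. Treatment length alone.** Planned exposure can differ by 90/42 = 2.14 times. With a constant daily risk, a 90-day risk p becomes 1 − (1 − p)^(42/90) over 42 days. Risks of 5%, 10% and 20% become 2.4%, 4.8% and 9.9%.

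**3. Case mix with no true age effect.** Assumed inputs, none of them in the documents: 10% risk over 90 days with cancer; daily risk without cancer equal (k = 1) or half (k = 0.5); one age group 80% cancer, another 10% cancer. From the protocol: d, the non-cancer treatment days, between 42 (6 weeks) and 90.

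- Non-cancer on-treatment risk: r = 1 − 0.9^(k·d/90)
- 80% cancer group: 0.8 × 10% + 0.2 × r
- 10% cancer group: 0.1 × 10% + 0.9 × r

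| d (days) | k | r | 80% cancer | 10% cancer | Ratio |
|---|---|---|---|---|---|
| 42 | 1 | 4.8% | 9.0% | 5.3% | 1.7 |
| 42 | 0.5 | 2.4% | 8.5% | 3.2% | 2.7 |
| 60 | 1 | 6.8% | 9.4% | 7.1% | 1.3 |
| 60 | 0.5 | 3.5% | 8.7% | 4.1% | 2.1 |
| 90 | 1 | 10.0% | 10.0% | 10.0% | 1.0 |
| 90 | 0.5 | 5.1% | 9.0% | 5.6% | 1.6 |

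The apparent age ratio therefore runs from 1.0 to 2.7. A second set of assumptions (20% v 80% cancer, 5% to 20% non-cancer 90-day risk, cancer hazard ratio 1 to 3) gives 1.5 to 2.5 at 42 days and 1.0 to 1.8 at 90 days.

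**4. Would an exposure-based rate alone be enough?** Take the half-risk case at 42 days. Mean planned days are 0.8 × 90 + 0.2 × 42 = 80.4 in one group and 0.1 × 90 + 0.9 × 42 = 46.8 in the other. In units of the cancer daily risk, the rates are (72 + 0.2 × 0.5 × 42)/80.4 = 76.2/80.4 = 0.948 and (9 + 0.9 × 0.5 × 42)/46.8 = 27.9/46.8 = 0.596, a ratio of 1.59. Kaplan-Meier estimates at Day 42 give (0.8 × 4.8 + 0.2 × 2.4)/(0.1 × 4.8 + 0.9 × 2.4), which is 1.62 before rounding. Person-time removes the length effect (the ratio is 1.0 when daily risks are equal) but not the risk effect. The split by cancer status is needed as well.

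**5. Can the planned models do the separation?** Using the Schoenfeld formula, two-sided 5%, 80% power for a cancer hazard ratio of 3 needs 27 events with a 50:50 cancer split or 41 with 20:80. With 5 events power is 16–23%; with 10 events, 28–41%. Under SAP censoring, a child treated for 42 days and followed to Day 90 has 42/90 = 47% of counted time on treatment. Minor bleeding and thrombus outcome have no adjusted analysis in either document.

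**The case against.** The strongest reply is that the plan already looks beyond crude proportions. Kaplan-Meier and Cox analyses are planned for recurrent VTE and major bleeding, and the protocol puts tumor type beside age group. The protocol synopsis also summarises major bleeding monthly. SAP 6.2.1 tabulates diagnosis of cancer by age group, and SAP 6.2.3 does so for treatment duration, so a reader can see an imbalance. All of this stands. A reader might infer from the tables that VTE and bleeding are reported only as crude proportions; the documents do not support that.

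The safeguards are looser than they look. The SAP does not carry over the protocol's Cox factors or the monthly summary. Tumor type is not the same as cancer yes/no, and neither document says how non-cancer children would be coded. The baseline table can reveal an imbalance but cannot remove it from the outcome tables.

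The second reply is that the practical weight is low. Assuming about 10 children per age group, 9.0% against 5.3% is 0.9 against 0.5 expected events, and 1/10 has an exact interval of 0.3% to 44.5%. No hypotheses are tested. This also stands and limits the severity, although a wide interval conveys imprecision, not confounding.

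Third, the objective's mention of cancer may describe who is enrolled rather than promise a comparison. That reading is possible, and the point does not depend on rejecting it.

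**Conclusion.** The point holds in limited form. The on-treatment VTE, thrombus-outcome and bleeding proportions have no cancer split and no allowance for exposure, and the SAP's models and censoring rule do not reliably separate age from cancer status or treatment length.

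The illustrated false age ratio is 1.0 to 2.7. It rests on an assumed 10% risk over 90 days, an equal or halved daily risk without cancer, cancer shares of 80% and 10%, and 42 to 90 days of non-cancer treatment. The upper end requires every non-cancer child to be treated for the shortest planned time.

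Two stronger readings are not supported. A reader might infer that the trial will show a false age gradient, but the documents give neither the cancer share by age nor a cancer hazard ratio, so this is a risk rather than a demonstrated bias. A reader might also extend the point to median dose and range achievement. The documents give no reason to expect these to differ by cancer status, and the population PD analysis already explores further covariates under a separate plan.

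The endpoints are secondary and descriptive. The change is worth making because it is cheap, not because a main conclusion is in danger.

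**What to change.** In SAP 3.3.2, 6.1.2.1, 6.3.1 and Appendix 1.1:

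1. Present VTE, thrombus outcome, and major and minor bleeding by baseline cancer status (yes/no) as well as by age group, with age-by-cancer cells shown as counts.
2. Add events per patient-time on dalteparin for VTE and for major and minor bleeding, overall, by age group and by cancer status.
3. For the on-treatment Kaplan-Meier and Cox analyses, censor at end of dalteparin treatment instead of the latest database date.
4. Name cancer status beside age in the SAP Cox and logistic models, where the number of events permits.
5. Label age contrasts as descriptive and not adjusted for cancer status.

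A cancer split of median dose and range achievement is optional.

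The cost is SAP wording and a few extra descriptive tables; cancer diagnosis and dosing data are already collected. Age-by-cancer cells will be small, which is why counts are proposed there. Events after dalteparin is stopped drop out of the time-to-event analyses, as the on-treatment definition implies.
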